 - 2. Reduction in kidney function (increase in creatinine or decrease in glomerular filtration rate)
 - 3. Very rarely causes dry cough
 - 4. Facial swelling (angioedema)

RN BP ASSESSMENT

- 1. RN BP Assessment Visit
 - a. Pre-Visit Planning: perform 1-2 weeks prior to appointment.
 - i. Call patient
 - 1. Request patient bring all pill bottles to appointment.
 - 2. If patient has home blood pressure device, ask patient to bring home device and written home blood pressure log (after checking blood pressure twice daily for 1 week) to appointment.
 - ii. GFR Assessment
 - 1. Review prior labs in "Results Review".
 - 2. Review last potassium, creatinine and glomerular filtration rate (GFR) in last 6 months.
 - 3. If all present within 6 months, no further action needed for GFR assessment.
 - 4. If no creatinine and GFR in last 6 months, order "CREATININE with-GFR".
 - 5. If no potassium in last 6 months, "POTASSIUM LEVEL".
 - 6. Compare most recent GFR with second most recent GFR. If most recent GFR is > 20% lower, discuss with provider.
 - 7. If GFR < 60 but >/= 30, update problem list to include "CKD Stage 3"
 - 8. If GFR < 30 but >15, update problem list to include "CKD Stage 4".
 - 9. If GFR < 15, update problem list to include "CKD Stage 5"
 - iii. Proteinuria Assessment
 - 1. Review prior urine protein testing in "Results Review" for following results in last 1 year:
 - a. Microalbumin/Creatinine Ratio, Urine, Random
 - b. Protein, Urine and Creatinine, Urine (both are required as ratio must be calculated manually by dividing urine

- protein by urine creatinine).
- c. Protein, 24 hour, Urine
- d. Urine dipstick protein (adjusted for specific gravity)
- 2. If labs are present in last year, no further action is needed for Proteinuria Assessment.
- 3. If none are available, order MICROALBUMIN/CREATININE RATIO

NOTE: "Unable to calculate" for Microalbumin/Creatinine Ratio implies zero protein present in urine.

- b. Assessment of BP goal
Goal blood pressure is SBP < 140 mmHg AND DBP < 90 mmHg.
- c. Provide education annually on non-pharmacologic management of hypertension.
 - i. Low Sodium Diet
 - 1. Discuss with patient importance of low sodium diet included no added salt as well as checking labels for processed foods.
 - 2. Provide patient with Exit Care SmartText in Patient Instructions: DIET-2 GRAM LOW SODIUM (choose appropriate language).
 - 3. Refer to nutrition at same clinical site for further counseling as needed.

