- a If patient is already on ACEi or ARB but not at maximum tolerated dose (see above), increase dose to achieve SBP and DBP goal (as per ACEi/ARB PROTOCOL below)
- b If patient is on maximum tolerated dose of ACEi or ARB, proceed to NON ACEi/ARB PROTOCOL.
- c If patient is not on ACEi or ARB, confirm allergies with patient.
- d If no prior allergy or adverse reaction to ACEi or ARB, proceed to ACEi/ARB PROTOCOL.
- e If prior allergy to ACEi is cough, proceed to ACEi/ARB PROTOCOL.
- f If prior allergy or adverse reaction to ACEi or ARB other than cough, consult with provider safety of starting ACEi or ARB.
- g If after discussion with provider, ACEi and ARB are both considered contraindicated, update allergies as needed

and proceed to NON-ACEi/ARB PROTOCOL.

ACEi/ARB PROTOCOL

1. Consider this protocol active until completed.
2. Review "Results Review" for past potassium and creatinine (abbreviated as "Cr" and "K" respectively hereafter). If both are available, no further action is needed. If one or both is not available in last 3 months, order both CREATININE LEVEL and POTASSIUM LEVEL as appropriate (referred to as "Cr/K Check" hereafter).
 - a. Lab Results Interpretation
 - i. Is K > 4.9?
 1. Yes
 - a. Discuss with provider before starting or increasing ACEi or ARB.
 2. No
 - a. If not on ACEi/ARB, and no prior allergy to ACEi or ARB, route pended order to provider for lisinopril 5mg once daily and proceed to "Follow-Up" below.
 - b. If not on ACEi or ARB and prior cough due to ACEi but no other ACEi or ARB allergy, route pended order to provider for losartan 25mg once daily and proceed to "Follow-Up" below.
 - c. If already on ACEi or ARB, but not at maximum tolerated dose, increase dose and proceed to "Follow-Up" below.
 - d. If already on ACEi/ARB at maximum tolerated dose, consider this protocol COMPLETED and proceed to NON-ACEi/ARB PROTOCOL.
 - e. Follow-Up
 - f. Schedule RN BP Assessment Visit and Cr/K Check 1-3 weeks following initiation or dose increase. Request patient to have labs drawn prior to appointment.
 - b. K Interpretation
 - i. Is K > 5.4?
 1. Yes. Discuss with provider stopping ACEi/ARB
 2. No
 - ii. 1. Is K > 4.9?
 3. Yes
 - a. Continue ACEi/ARB at current dose.
 - b. Provide patient with low potassium diet handout
 - c. Order repeat POTASSIUM LEVEL in 1 week.
 - d. If K is not < 5.0 on repeat evaluation, discuss with provider.
 - e. If K is </= 4.9, proceed to Cr Interpretation.
 4. No - proceed to Cr Interpretation.

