- c. Serum Creatinine (Cr) Interpretation
 - ii. Is Cr >20% higher than value prior to initiation or last increase of ACEi/ARB?
 - 1. Yes. Discuss with provider decreasing dose by 50% (or stopping if at starting dose). Discuss follow up plan for Cr with provider as well.
 - 2. No
 - (i) Is creatinine within 30% of baseline since initiation?
 - (a) No. Discuss with provider decreasing dose by 50% (or stopping if at starting dose). Discuss follow up plan for Cr with provider as well.
 - (b) Yes. Proceed to RN BP Assessment.
 - 3. RN BP Assessment
 - a. Perform RN BP Assessment as detailed above.
 - b. Is BP at goal based on definitions above?
 - i. Yes. Continue regimen and schedule RN BP Assessment Visit in 3 months and follow-up with PCP within 6 months.
 - 1. If BP continues to be at goal in 3 months, this protocol is COMPLETE and can return hypertension management to PCP.
 - ii. No
 - 2. Is ACEi/ARB at maximum tolerated dose?
 - (i) Yes. This protocol is COMPLETE. Initiate NON-ACEi/ARB PROTOCOL.
 - (ii) No route pended order to provider for double prior dose of current ACE and return to "Follow-Up" above.

NON ACEi/ARB PROTOCOL

- 1. Discuss with provider selection of next anti-hypertensive protocol.
- 2. Discuss following medication suggestions with provider. These are only suggestions to guide management, but final selection is at provider's discretion.
 - a. If patient has history of myocardial infarction or heart failure, recommend BETA-BLOCKER PROTOCOL.
 - i. Recommend carvedilol given dual properties of heart rate reduction (beta blockade) and vasodilation (alpha blockade) and, therefore, typically greater impact on blood pressure.
 - ii. Recommended starting dose: carvedilol 6.25mg twice daily.
 - iii. Maximum dose: carvedilol 25mg twice daily.
 - iv. Class-specific considerations
 - 1. Low heart rate (bradycardia)
 - 2. Lower extremity swelling, erectile dysfunction, fatigue.
 - 3. Exacerbation of asthma or chronic obstructive lung disease symptoms (shortness of breath or wheezing).
 - b. If patient is on maximum tolerated beta-blocker or has no history of myocardial infarction or heart failure, recommend DIURETIC PROTOCOL.
 - i. For patients with GFR > 30 mL/min, recommend chlorthalidone.
 - 1. Starting dose 12.5mg once daily.
 - 2. Maximum dose 25mg once daily. However, dose adjustment is dependent on provider assessment of volume status. All follow-up

evaluations should be discussed with provider.

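### Appendix I, ACEi/ARB PROTOCOL step 2a: the entry creatinine has no action rule before a first start or entry dose increase; only potassium has one (minor safety wording)

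*Combined protocol and SAP*

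**What the plan says.** All of this is in Appendix I, the nurse-run CKD hypertension protocol for the intervention arm.

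- **Before the visit.** The GFR Assessment belongs to a block headed "Pre-Visit Planning: perform 1-2 weeks prior to appointment". Item 3 reads "If all present within 6 months, no further action needed for GFR assessment". Items 4 and 5 order labs only when none exist in that window. Item 6 compares the two latest GFR values: "If most recent GFR is > 20% lower, discuss with provider".
- **At the visit, before Medication Adjustment.** Item f of the Home Blood Pressure Log Review asks about adverse effects, including the class-specific ones, and refers any new one to the provider.
- **Entry to the ACEi/ARB PROTOCOL, step 2.** Potassium and creatinine are looked up, now on a shorter window: "If one or both is not available in last 3 months, order both CREATININE LEVEL and POTASSIUM LEVEL as appropriate".
- **Step 2a, Lab Results Interpretation.** The only laboratory question is whether K is above 4.9. If yes: "Discuss with provider before starting or increasing ACEi or ARB". If no, a patient not on treatment and without an allergy gets "route pended order to provider for lisinopril 5mg once daily". For a patient already treated: "If already on ACEi or ARB, but not at maximum tolerated dose, increase dose and proceed to" follow-up.
- **Follow-up, 1 to 3 weeks after the start or increase, step 2c.** The first creatinine rule of this protocol appears: "Is Cr >20% higher than value prior to initiation or last increase of ACEi/ARB". A second question asks whether creatinine is within 30% of a baseline that is not defined further.

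**The concern.** The protocol obtains two laboratory values for one decision and gives a rule to only one of them. A nurse who follows step 2a as written takes a patient with a newly raised creatinine and K of 4.9 or lower to a pended first dose, or to a dose increase, without being told to raise the creatinine with the provider.

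There is a second effect. The entry creatinine is the reference for the 20% check at follow-up. If it is already raised and nobody has remarked on it, later change is measured from the raised value.

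What is at stake is patient safety in the active arm. Section 9.1 lists acute kidney injury, eGFR falls of at least 50% and start of dialysis among the events that could be related to the interventions. The appendix's own DIURETIC PROTOCOL handles the same situation differently: it orders potassium and creatinine with eGFR if older than three months, and branches on both (K above 3.5, GFR above 30) before a drug is chosen.

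**Working it through.** The plan states no figure on this point, so the check is a trace through the decision path, followed by arithmetic on a hypothetical case and on the cost of the fix.

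**Which creatinine values escape an earlier rule?** Item 3 is read here as meaning that no new order is needed.

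| Age of last labs | Pre-visit GFR Assessment | Step 2 | Is the entry creatinine tested by a change rule before dosing? |
|---|---|---|---|
| Under 3 months | No order; item 6 compares GFR | No order | Yes, through item 6 |
| 3 to 6 months | No order; item 6 compares the old values | New creatinine ordered | **No** |
| Over 6 months | New labs ordered; item 6 can compare them | No order if results are back | Yes, through item 6 |

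The gap is mainly the middle row. If item 3 is instead read as ending the assessment, item 6 is skipped as well whenever labs are present, and the gap is wider.

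The adverse-effect review does not fill the middle row. For a patient already on treatment it precedes Medication Adjustment, and so precedes a creatinine first ordered at step 2. For a patient not yet on treatment, the appendix ties the kidney-function item to follow-up of initiation or titration.

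**Illustration (hypothetical values, not from the documents).** Creatinine is 1.4 at 10 months and 1.4 at 4 months before the visit, so item 6 does not flag. Step 2 orders new labs: creatinine 2.1, K 4.8.

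- Rise at entry: 2.1 / 1.4 = 1.50, or +50%. K is not above 4.9, so lisinopril 5 mg is pended.
- Follow-up creatinine 2.5: 2.5 / 2.1 = 1.19. The 20% limit is 2.1 × 1.20 = 2.52, so there is no flag.
- 30% check, if baseline means 2.1: limit 2.1 × 1.30 = 2.73, no flag.
- 30% check, if baseline means 1.4: limit 1.4 × 1.30 = 1.82, flag. The total rise is 2.5 / 1.4 = 1.79.

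The follow-up value was chosen to lie just under the 20% limit. The case shows the mechanism, not its frequency. With a creatinine question at entry, the limit would be 1.4 × 1.20 = 1.68, and 2.1 would be raised before dosing.

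**Cost of that question in stable patients.** Take two independent lognormal readings with the same within-person CV. The SD of the log ratio is √(2 ln(1 + CV²)), and the chance of a false flag is P(Z > ln 1.20 / SD), with ln 1.20 = 0.1823. The CVs are assumptions.

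| CV | SD of log ratio | z | Flagged by noise |
|---|---|---|---|
| 5% | 0.0707 | 2.58 | 0.5% |
| 8% | 0.1130 | 1.61 | 5.3% |
| 10% | 0.1411 | 1.29 | 9.8% |

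**The case against.** The strongest reply is that a clinician is already in the loop.

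- The appendix's introduction leaves the choice of drug and dose to the provider, and a first start reaches the provider as a pended order.
- Section 9.2.5 sends abnormal laboratory findings to the primary care provider under each system's own procedures. Section 7.3 directs captured creatinine and eGFR data to primary care teams.
- The protocols are optional for practitioners (section 6.5).
- The parent CKD protocol that triggers Appendix I, and the manual described in section 13.1, are not in the documents. Either might hold a creatinine instruction.
- The baseline in the 30% check can reasonably be read as the value at initiation.

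Most of this stands, and it is why the point is minor. It does not remove the point. The general safeguards cover potassium equally, yet the authors still wrote a potassium rule at this step. None of them sets a threshold for change in creatinine or is tied to the dosing decision. Reading baseline as the value at initiation leaves the raised entry value as the reference, which is the less protective choice.

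A reader might infer that Appendix I has no renal check at all before a start. The documents do not support that: item 6 exists, the adverse-effect review exists, and the background section lowers the lisinopril starting dose when GFR is below 10. Nor is the entry creatinine collected for nothing, since it serves as the follow-up reference. Later doublings in the titration loop do pass through the creatinine checks.

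**Conclusion.** The point holds as a cheap improvement of low severity. Step 2a has no creatinine rule before a first start or an entry dose increase. The gap not covered by earlier steps is mainly a creatinine first drawn at step 2 because the last labs are 3 to 6 months old, with K of 4.9 or lower and a real rise since the previous value.

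The absence of the rule is plain from the text. Its practical reach is not known: the documents do not say how many patients have labs of that age or a rising creatinine. A reader might be tempted to size the problem from the pilot in section 2.2.3, where ACEi/ARB use rose from 57.8% to 87.2% of 107 patients. That figure shows only that starts were common in another study. It counts neither entries under step 2a nor missed rises, so no number of patients harmed can be derived from it. Nor does the point touch the trial's inference: eligibility, power and analyses are unaffected.

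The conclusion rests on reading item 3 as meaning that no new order is needed, and on no creatinine rule being present in the parent protocol or the manual.

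**What to change.** Three wording changes in Appendix I, carried into any SmartSet built on it:

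1. In step 2a, beside the potassium question, add: *Is the latest Cr (including one ordered in step 2) more than 20% above the previous value?* If yes, use the action already written for potassium: "Discuss with provider before starting or increasing ACEi or ARB".
2. Reword GFR Assessment item 3 to: *no new order needed; go to item 6*.
3. In step 2c, define baseline as the last creatinine before the first ACEi/ARB dose or, if that value was flagged under change 1, the creatinine before it. In the illustration this sets the baseline at 1.4 and the 30% limit at 1.82.

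No new tests are needed, because the values are already retrieved or ordered. The price is extra provider discussions, including those triggered by noise in about 0.5% to 10% of stable patients under the assumed CVs of 5% to 10%, and a few delayed starts. The action is a discussion, not a bar to treatment, so it does not conflict with the appendix's aim of ACEi or ARB treatment for all patients with CKD. If the parent protocol or the manual already contains such a rule, a cross-reference in step 2a would be enough in place of change 1.

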 - ii. Avoidance of daily use of non-steroidal anti-inflammatory drugs (NSAIDs).
 - 1. Discuss with patient that NSAIDs (included ibuprofen and naproxen) can increase blood pressure as well as cause further kidney damage.
 - 2. Discuss with provider as needed to identify alternatives to daily NSAIDs.
 - iii. Moderation of alcohol (less than 2 servings per day).
 - 1. Discuss with patient that daily alcohol consumption can raise blood pressure.
 - 2. If needed, provide patient with Exit Care SmartText in Patient Instructions: ALCOHOL AND DRUG ABUSE (choose appropriate language).
 - 3. Refer for substance abuse counseling as needed.
 - iv. Importance of exercise > 3 days per week.
 - 1. Discuss with patient that regular exercise can lower blood pressure.
 - 2. Provide patient with Exit Care SmartText in Patient Instructions: PKAMB OPC EXERCISE TO LOSE WEIGHT
 - v. Abstinence from nicotine products.
 - 1. Discuss with patient that all nicotine products can raise blood pressure.
 - 2. If active smoker, perform 'Ready to Quit' assessment in social history section Epic and refer to Smoking Cessation Clinic if

patient is ready to quit.

3. Provide patient with Exit Care SmartText in Patient Instructions: SMOKING CESSATION (choose appropriate language).

vi. Maintenance of optimal weight is body mass index (BMI) 20.0 to 25.0.

1. Discuss with patient that maintenance of normal BMI can improve blood pressure.
2. If BMI > 25.0
 - (a) Provide patient with both of following Exit Care SmartText in Patient Instructions: DIET—CALORIE COUNTING (choose appropriate language) and DIET— LOW-FAT, LOW-SATURATEDFAT, LOW-CHOLESTEROL DIETS (choose appropriate language)
3. Refer to nutrition at same clinical site as needed for dietary counseling.

vii. Avoidance of daily use of over-the-counter decongestants (pseudoephedrine or phenylephrine).

1. Discuss with patient that prolonged use of decongestants can raise blood pressure.
2. Discuss with provider as needed for alternatives to decongestants for control of symptoms.

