 - 3. If difference < 10 mmHg (systolic or diastolic), under CKD diagnosis in Problem List, record in Overview section: "Home BP Device Validation [DATE]: home device validated as consistent with RN measurement" and proceed to "Home Blood Pressure Log Review".

5. Home Blood Pressure Log Review

- a If BP cuff is validated as above and home BP log is used in clinical decision-making, log should be scanned into Epic.
- b Calculate average of seven most recent systolic and diastolic values (i.e. sum of seven most recent systolic values divided by 7; and sum of seven most recent diastolic values divided by 7).
- c If average systolic > 140 mmHg or average diastolic > 90 mmHg, initiate CKD HYPERTENSION PROTOCOL and perform at this visit.
- d If average systolic < 140 mmHg AND average diastolic < 90 mmHg, no further action is necessary.
- e Consider extenuating circumstances such as acute pain and acute psychological distress. Discuss with provider if you feel such extenuating circumstances are contributing to blood pressure elevation. Consider rescheduling RN BP Assessment Visit in 2-4 weeks to reassess.

- f Assess for adverse effects every visit including class-specific considerations above as well as side effects common to many blood pressure medications which include (but are not limited to) lightheadedness and fainting.
 - (i) If any new adverse effects, discuss with provider.
 - (ii) If no new adverse effects, proceed to BP Medication Adherence Assessment.
- g BP Medication Adherence Assessment
 - (i) Ask patient about each BP medication and ask, "How many days per week do you forget your [insert BP medication]?"
 - (ii) If one day or less, consider adherent by self-report.
 - (iii) Review BP medication bottles if available.
 - (iv) If medications are filled at Parkland pharmacy, review refill history in Cerner for last 6 months. Consider adherent if obtains within 6 days for a 30 day prescription or within 18 days for a 90 day prescription.
 - (v) If not adherent by self-report or refill history, discuss with patient importance of adherence.
 - (a.) Reschedule RN BP Assessment Visit in 2 weeks after improved adherence.
 - (b.) If patient was deemed non-adherent on two consecutive visits, refer to clinical pharmacist for medication review and assistance with barriers to adherence (cost, complexity, etc).
 - (vi) If considered adherent by self-report and refill history, proceed to "Medication Adjustment".

6. Medication Adjustment

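### Appendix I has no pregnancy question before its four ACEi/ARB start or increase actions, although pregnancy on these drugs is a listed safety event

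*Combined protocol and SAP*

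**What the plan says.** Appendix I states under Goals/Background that every patient with CKD should receive an ACE inhibitor or ARB, and gives no exception for pregnancy. Its ACEi/ARB PROTOCOL then contains four instructions that start a drug or raise its dose:

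- start an ACE inhibitor: "If not on ACEi/ARB, and no prior allergy to ACEi or ARB, route pended order to provider for lisinopril 5mg once daily";
- start an ARB after an ACE inhibitor cough: "route pended order to provider for losartan 25mg once daily";
- raise an existing dose: "If already on ACEi or ARB, but not at maximum tolerated dose, increase dose";
- at a repeat visit with blood pressure still above goal: "No route pended order to provider for double prior dose of current ACE".

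Medication Adjustment step a also speaks of raising the dose, "increase dose to achieve SBP and DBP goal (as per ACEi/ARB PROTOCOL below", but it only refers the nurse to the third instruction.

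Sections 2.3 and 9.1 list pregnancy during ACE inhibitor or ARB treatment among the events to be captured. Section 9.1 gives the reason: the listed events could be related to the interventions. Section 2.3 says they go to the DSMB each quarter for the intervention group. The Protocol Summary admits men and women aged 18 to 85. Section 5.2 excludes by age and by CKD stage 5/ESRD, not by pregnancy.

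**The concern.** The plan foresees exposure in pregnancy and sets up reporting for it, but the order pathway in Appendix I contains nothing that would catch a pregnancy before a new or higher dose is requested. A nurse who follows the text exactly can route an ACE inhibitor or ARB order for a pregnant woman without having asked. The matter then depends on the provider, PA or NP thinking of it unprompted, or on a question in another appendix. What is at stake is patient safety in the intervention arm, not the validity of the comparison between arms.

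**Working it through.** No arithmetic beyond counting applies, and the plan gives no figure to reproduce. The check sets the texts side by side.

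**1. What must be true before each action.** The nurse reaches medication changes only when blood pressure is above goal and the patient is judged adherent. The remaining conditions are:

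| Action (Appendix I, ACEi/ARB PROTOCOL) | Written conditions | Pregnancy asked? |
|---|---|---|
| Start lisinopril | Potassium not above 4.9; not on either class; no prior allergy | No |
| Start losartan | Potassium not above 4.9; not on either class; prior ACE inhibitor cough and no other allergy | No |
| Increase dose | Potassium not above 4.9; below maximum tolerated dose | No |
| Double dose | Follow-up potassium and creatinine acceptable; blood pressure not at goal; below maximum tolerated dose | No |

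That is 3 actions in the branch for acceptable potassium plus 1 doubling step, 4 in all, and 0 of the 4 have a pregnancy question before them. Counting the pointer in Medication Adjustment a would make 4 + 1 = 5 written instructions and would change nothing.

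**2. Where pregnancy appears in the documents.** Sections 2.3 and 9.1 name it as a safety event. The Checklist for Patient Visits in Appendix II asks about it, and also gives it as an example of a contraindication to statins. Appendix I does not mention it. Its class-specific considerations for lisinopril and losartan cover raised potassium, reduced kidney function, cough and angioedema only.

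**3. A patient walked through the text.** Take a pregnant woman above the blood pressure goal, adherent, with no allergy and potassium of 4.9 or lower. If untreated, she meets the conditions for the lisinopril order. If on a submaximal dose, she meets those for an increase. Medication Adjustment g does allow for both classes being contraindicated, but it is reached through step f, which concerns a prior allergy or reaction. She has none, so she is not sent there.

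**4. Where a prompt would have to sit.** Medication Adjustment comes before the first three actions. The doubling step is worded differently: it goes from the blood pressure goal to the maximum-dose question to the order, and names no return to Medication Adjustment. A prompt only at Medication Adjustment may therefore not precede the fourth action.

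**5. Who is missed by asking only at a start or increase.** Women already on the drug who are at blood pressure goal, or at maximum dose, have no start or increase to trigger the question. They may be numerous: in the pilot table of Section 2.2.3, 57.8% were already on ACEI/ARB at screening. That is a related but different population, so it is only an indication.

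**The case against.** The best defence has three parts.

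First, no nurse prescribes. The introduction to Appendix I leaves drug and dose to the provider, involves a PA or NP who may suggest deviations, and Section 9.1 gives primary care providers the last word on every intervention. Section 5.2 also lets practitioners withhold the intervention where risk is too high. All of this stands. But the provider also signs off when potassium is above 4.9 or there was a prior reaction, and Appendix I still writes a prompt for those, as it does for falling kidney function: "If most recent GFR is > 20% lower, discuss with provider". Sign-off alone was not considered enough for those hazards.

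Second, every trial patient has type 2 diabetes, Appendix II is written for exactly this population, and its checklist asks about pregnancy and points to the hypertension protocols. Section 6.5 allows all three protocols to be initiated together. This is a real safeguard where it is used. However, the question has no action attached, is not tied to ACE inhibitor or ARB orders, and sits in a protocol whose activation is optional.

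Third, Appendix I is started from a parent CKD protocol that is not reproduced, the manual of operation (Section 13.1) is a separate document, and the workflow and SmartSet figures are not shown. A check may exist there. That is correct, and it limits the point to the wording of Appendix I.

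A reader might infer that the plan contradicts itself, or that pregnant women will be given these drugs unchecked. Neither follows: this is an omission in one appendix, and a pended order is a request that the provider can refuse. A reader might also measure the gap by counting the other places where the nurse is told to consult the provider. Many of those, such as "Discuss with provider as needed to identify alternatives to daily NSAIDs" or "Discuss with provider if you feel such extenuating circumstances are contributing to blood pressure elevation", have no reason to mention pregnancy, so such a count adds no evidence.

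**Conclusion.** The point holds for Appendix I as written: four start or increase actions, none preceded by a pregnancy question, for an event that the plan itself says could be related to the interventions. It warrants a cheap improvement to a clinical protocol. It is not a flaw in the trial's statistics; the primary outcome analysis, power and error rates are unaffected.

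No number of affected women can be given, because the documents contain no data on sex, age distribution or pregnancy for the cohort. Exposure is narrower than the intervention arm: activation is optional, medication is adjusted only above the blood pressure goal, and parts of Appendix I are worded for Parkland. The conclusion assumes that the unseen parent protocol, manual and SmartSet do not already ask; if one does, what remains is a missing cross-reference.

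It would be tempting to say that a prompt at each start or increase deals with the listed safety event. It does so only in part, since women who simply remain on the drug would not be asked.

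**What to change.** For women who could be pregnant, add to Appendix I the question that Appendix II already contains (is she, or might she be, pregnant), with an action: if yes or possibly, do not pend or increase an ACE inhibitor or ARB; discuss with the provider, including whether to stop one already in use. Put it in two places:

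1. at the top of Medication Adjustment, before steps a and b, so that women already at maximum dose are asked too;
2. immediately before the doubling order in the ACEi/ARB PROTOCOL.

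Asking the same question with the adverse-effect check made at every visit (Home Blood Pressure Log Review, step f) would also reach women who stay on the drug at goal. The text should then say that it applies at goal, since the steps before it tell the nurse that no further action is needed there.

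If the parent protocol, manual or SmartSet already asks, cite that step in Appendix I instead. The cost is one extra question per relevant visit and a short delay to the order when the answer is yes or possibly. Eligibility, sample size and analysis do not change.
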